9. STATISTICAL CONSIDERATIONS

9.1. General Statistical Considerations

The data cutoff for the primary analysis will occur after all subjects have either discontinued the study or completed at least Week 25 assessments. The final analysis of the study will occur after all subjects have discontinued the study. Data collected beyond the primary analysis cut-off time point will be presented as appropriate in a CSR addendum.

The data cutoff for safety and PK analysis in Part 1 will occur after all subjects have received pexidartinib and have either completed the minimum safety evaluation requirements over the DLT evaluation period (28 days) or have experienced a DLT during the DLT evaluation period.

Data analysis will also be conducted separately by Part 1 and Part 2. The pooled analysis may be planned in the Statistical Analysis Plan (SAP).

Continuous variables will be summarized by the number of observations, mean, standard deviation, median, 25th and 75th percentile, and minimum and maximum values. Categorical variables will be summarized using frequency counts and percentages.

Assessments of change from baseline to post-treatment or the ratio of post-treatment to baseline will include only those subjects with both baseline and post-treatment measurements. The last non-missing value of a variable taken before the first dose of the study drug will be used as the baseline value, unless otherwise specified. In general, missing or dropout data will not be imputed for the purpose of data analysis, unless otherwise specified.

For the primary and secondary efficacy endpoints, with the exception of duration of response, the point estimate and accompanying 95% CI will be computed. For duration of response, Kaplan-Meier product limit methodology will be utilized to provide estimates, including those for the median and 25th and 75th percentiles.

No formal interim analysis is planned in Part 1 or Part 2.

For all analysis, the Part 1 data at the end of Part 1 will be used.

The all analysis including the efficacy analysis of the subjects in Part 1 was originally planned to be performed at the end of Part 2. However, the sponsor decided not to proceed with Part 2. Depending on this decision, the Part 1 data will be analyzed at the end of Part 1, and the efficacy analysis will be performed as the exploratory analysis.

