| | Description: PRO relevant to the assessment of the "worst" pain in the last 24 hours | (ie, 30% or more improvement in average NRS) | |
| | Time frame: Week 25 | | |
| | Title: BOR based on RECIST 1.1 Description: BOR as assessed by centrally reviewed MRI scan based on RECIST 1.1 Time frame: At the time of the primary analysis: After all subjects have made the Week 25 visit or have discontinued from the study, whichever occurs first | BOR is defined as the proportion of subjects who achieved CR, PR, SD, PD, and NE recorded as the best response based on RECIST 1.1 by centrally reviewed MRI scan | Efficacy |
| | Title: BOR based on TVS Description: BOR as assessed by centrally reviewed MRI scan based on TVS Time frame: At the time of the primary analysis | BOR is defined as the proportion of subjects who achieved CR, PR, SD, PD, and NE recorded as the best response based on TVS by centrally reviewed MRI scan | Efficacy |
| | Title: DoR based on RECIST 1.1 Description: DoR as assessed by centrally reviewed MRI scan based on RECIST 1.1 Time frame: At the time of the primary analysis | DoR is defined as the time from the date of the first recorded response to the first date of documented disease progression | Efficacy |
| | Title: DoR based on TVS Description: DoR as assessed by centrally reviewed MRI scan based on TVS Time frame: At the time of the primary analysis | DoR is defined as the time from the date of the first recorded response to the first date of documented disease progression | Efficacy |
| Part 1, Part 2: To assess the safety of pexidartinib | Title: TEAEs and other safety parameters during the study* Description: Descriptive statistics of safety endpoints Time frame: Continuous monitoring and reported at the time of each data cut-off *Though this is a secondary objective, this is a primary outcome measure | Safety evaluation include the following, but is not limited to: TEAEs, drug induced hepatotoxicity, laboratory tests, vital signs, and ECGs | Safety |
| Part 1, Part 2: To evaluate the PK properties of pexidartinib | Title: PK profile Description: Plasma concentrations and PK parameters of pexidartinib and ZAAD-1006a | Plasma concentrations and PK parameters of pexidartinib and ZAAD-1006a, the major metabolite of pexidartinib | PK |

| Objectives | Outcome Measure | Endpoints | Category |
|---|--|---|----------|

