4.1.2. End of Study

The **primary completion date** is the date when all enrolled subjects have completed the predetermined duration of treatment (ie, the date when all DLT-evaluable subjects have either completed minimum safety evaluation requirements over the DLT evaluation period [28 days] or have experienced a DLT during the DLT evaluation period for Part 1, Week 25 for Part 2) or have discontinued the study. This date is used as the cut-off date for the analysis of the primary endpoint of the study. All subjects still on treatment and continuing to derive benefit from the

study drug at the Primary Completion Date will continue to follow the study schedule of assessments (Section 1.3) until the **overall End of Study (EOS)** is reached.

Overall EOS will occur when:

- the last subject last visit has occurred
- all subjects have discontinued treatment or discontinued the study or have died
- an alternative study becomes available for subjects continuing to derive benefit from treatment with pexidartinib, where the study drug is offered to these subjects
- the study is discontinued by the Sponsor for other reasons (administrative, program-level, or class-related)

The subject's EOS is the date of their last study visit/contact.

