9.5.1. Efficacy Analyses

Table 3.1 lists the primary and secondary efficacy endpoints and their corresponding definitions of all endpoints. Additional details for the analysis is noted in the following sections.

In June 2024, the sponsor decided not to proceed with Part 2. Therefore, the primary efficacy analysis and the secondary efficacy analysis will be performed as the exploratory efficacy analysis using Part 1 data.

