9.5.1.2. Secondary Efficacy Analyses

The secondary efficacy endpoints will be provided in Part 2:

- Proportion of TVS responders who achieve a CR or PR at Week 25 based on TVS by centrally reviewed MRI scan
- Mean change from baseline in ROM of the affected joint, relative to a reference standard for the same joint at Week 25
- Mean change from baseline in the PROMIS Physical Function Scale at Week 25
- Proportion of BPI responders based on the BPI Worst Pain NRS item and analgesic use by BPI-30 definition (subject who (i) experienced a decrease of at least 30% in the mean BPI Worst Pain NRS item and (ii) did not experience a 30% or greater increase in narcotic analgesic use when compared to baseline)
- Best overall response (BOR) based on RECIST 1.1 by centrally reviewed MRI scan
- BOR based on TVS by centrally reviewed MRI scan
- Duration of response (DoR) based on RECIST 1.1 by centrally reviewed MRI scan

• DoR based on TVS by centrally reviewed MRI scan

A brief description of each analysis is provided below:

- An estimate of the proportion of TVS responders and BPI responders and the two-sided 95% CI based on the Clopper-Pearson method will be calculated. Subjects who do not provide data for each endpoint will be considered to be non-responders.
- Change from baseline in ROM and PROMIS will also be summarized with point estimates and 95% CIs.
- The percentage and 95% CI will be provided for the BOR
- DoR will also be analyzed as a secondary endpoint and will be summarized only for responders based on RECIST 1.1 and TVS. For subjects who do not have radiological progression, the duration of response will be censored. Subjects not known to have experienced an event at the time of data cut-off will be censored at the date of the last tumor assessment before the cut-off date. The SAP includes additional censoring rules. The Kaplan-Meier product limit method will be used to compute the estimate and 95% CI of the median and 25th and 75th percentiles.

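### Does Section 9.1 leave the Part 1 data cutoff undefined and in conflict with its older 28-day cutoff?

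*Combined protocol and SAP*

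**What the plan says.** Section 9.1 holds four timing statements. Two are conditional cutoffs from the two-part design. For Part 1, "The data cutoff for safety and PK analysis in Part 1 will occur after all subjects have received pexidartinib" and have completed the 28-day DLT period or had a DLT. For the main efficacy analysis, "The data cutoff for the primary analysis will occur after all subjects have either discontinued the study or completed at least Week 25 assessments". A third places the final analysis after every subject has left the study, with data beyond the primary cutoff going to a CSR addendum. Version 4.0 added the fourth: "For all analysis, the Part 1 data at the end of Part 1 will be used".

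Section 4.1.2 splits the primary completion date by part ("DLT evaluation period for Part 1, Week 25 for Part 2"). It lists the events that mark overall end of study, the first being the last subject's last visit, and says that a subject's "EOS is the date of their last study visit/contact". Nothing states which event is the end of Part 1.

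Section 9.5.1 says that "the primary efficacy analysis and the secondary efficacy analysis will be performed as the exploratory efficacy analysis using Part 1 data". Section 9.5.1.2 says that duration of response (DoR) without an event "will be censored at the date of the last tumor assessment before the cut-off date". Table 3.1 gives best overall response (BOR) and DoR the time frame "At the time of the primary analysis: After all subjects have made the Week 25 visit or have discontinued from the study".

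**The concern.** Three dates appear in one section, and the one that now governs has no definition. The 28-day sentence covers Part 1 safety and PK without qualification. Yet Part 1 has secondary objectives that run well past Day 28: sparse PK at C2D1, C3D1 and C5D1, and continuous safety monitoring. If a programmer locked the data on the last subject's Day 28, the main Part 1 tables would be truncated for anyone dosed late. DoR censoring depends on a cutoff date, so its follow-up could range from weeks to well over a year. In an open-label study, a date left open might also be chosen after the results are known.

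**Working it through.** The plan gives no figure on this point. Its only power statement belongs to the cancelled Part 2 and does not depend on the cutoff.

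**What a Day 28 lock would lose (last-dosed subject only).** Visit days follow from Table 1.1:

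- C2D1 is Day 29 (27 to 31 with its ±2-day window), C3D1 is Day 57, C4D1 (Week 13) is Day 85, C5D1 is Day 113 and C7D1 (Week 25) is Day 169. The last four have ±7-day windows.
- Sparse PK (Table 8.3): 3 visits × 2 samples = 6. C3D1 and C5D1 fall outside (4 samples); C2D1 is borderline (2).
- Liver tests after C1D1 up to Week 25: 4 visits inside, 1 borderline (C2D1) and 9 outside; 4 + 1 + 9 = 14.
- The DLT endpoint and the 8 + 6 = 14 intensive PK samples at C1D1–C1D2 and C1D15 all fall within Cycle 1, so no reading affects them.

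**Whether the text requires that lock.** It does not. The cutoff comes after a condition is met, so Day 28 is the earliest permitted date. The Week 25 sentence works the same way, since it asks for at least the Week 25 assessments. A snapshot at Week 25 or later takes in all six sparse samples, because the latest C5D1 is Day 113 + 7 = 120 and the earliest Week 25 visit is Day 169 − 7 = 162. The last of the 14 liver-test visits is the Week 25 visit itself. One later snapshot therefore satisfies both older sentences and the Version 4.0 sentence.

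**Which end date.** The DLT period is ruled out as the end of Part 1, because Section 9.5.1 runs efficacy on Part 1 data and Table 8.1 needs MRI at Weeks 13 and 25. Two natural candidates remain: all subjects off treatment, or the last subject's last visit. The End of Study visit is 12 weeks ± 7 days after the last dose, so they differ by 84 days, or 84 + 7 = 91 at most.

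**Which results move with the date.** Response rate, range of motion, PROMIS and BPI are fixed at Week 25, so they do not move once that visit has passed. BOR, DoR and cumulative safety do. Four DoR analyses are planned. Three are centrally read: RECIST and TVS in Section 9.5.1.2, and modified RECIST-SSD in Section 9.5.1.3. Section 8.3 stops central reading from Version 4.0, so any cutoff after that amendment gives the same centrally read DoR. Only locally read RECIST DoR stays open.

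**Size for locally read DoR.** At the earliest Week 25 cutoff, a subject responding at Week 13 has 169 − 85 = 84 days of follow-up (162 − 92 = 70 to 176 − 78 = 98 with windows). For the late end an enrolment date must be assumed, as none is given:

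- Enrolment on 30 June 2024 and first dose 3 days later (Table 1.1, footnote f) put C1D1 at 3 July 2024, Day 28 at 30 July 2024 and Week 13 at 25 September 2024.
- Last dose on 28 February 2026 plus 84 days gives 23 May 2026.
- From 25 September 2024 to 23 May 2026 is 605 days. Both visits have ±7-day windows, so the range is 605 ± 14, or 591 to 619.
- Earlier first dosing with the same stop date lengthens this; earlier stopping shortens it.

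Even on this late-enrolment calendar, Day 28 (30 July 2024) falls before Version 4.0 (27 August 2024). The 28-day condition had been met when the new sentence was written.

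**The case for a change.** The best argument for a change is that no reading is tidy. If the end of Part 1 is the DLT period, the efficacy analyses cannot be done. If it is later, an unqualified 28-day sentence stands beside a rule for all analyses. Section 4.1.2 lists several end-of-study events without saying whether the first or the last counts. A definition would cost a few words and would remove any freedom to pick a favourable snapshot. Hepatotoxicity adds weight: Section 2.3 places observed cholestasis in the first 8 weeks, and Day 28 covers only half of that.

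Part of this stands. The term is undefined, and Version 4.0 did not reconcile the older sentences or the Table 3.1 time frame with it. The rest carries less. The first branch is excluded by the plan itself, and the second is not a conflict, because both older sentences permit a later date. The 28-day review served the decision to open Part 2, which is now moot, and Table 3.1 reports safety at each data cutoff, so more than one snapshot is foreseen. A Day 28 lock as the only safety report would need a reader to ignore the Version 4.0 sentence. As for picking a date, no threshold or test can be crossed, Section 9.5 requires the SAP before database lock, and later data can go to an addendum.

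Moving BOR and DoR from the Week 25 time frame to the last visit would be more than clarification. It would let later scans enter BOR, which is a different choice of endpoint and not the repair of a wrong rule.

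**Conclusion.** No change to the plan is needed. The older cutoffs are leftovers that set earliest dates, and a snapshot at the end of Part 1 satisfies them. With Part 2 cancelled, the last subject's last visit and the final analysis after all subjects leave the study supply a workable end point, which analysts can name in the SAP.

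The remaining uncertainty is 84 days (up to 91) between last dose and the End of Study visit. If Table 3.1's Week 25 time frame were kept for DoR, a Week 13 responder would have 84 days of follow-up, against 605 under the assumed calendar. That difference is confined to locally read RECIST DoR, provided the cutoff falls after Version 4.0. All of it concerns descriptive or exploratory results in nine subjects.

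This rests on two assumptions: that the Version 4.0 sentence governs, as its wording and stated reason indicate, and that the SAP names the date before lock. No separate SAP text was available to confirm the second. The calendar figures are illustrations, not maxima.

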9.2. Statistical Hypothesis

In Part 1:

The following is the hypothesis in Part 1, but there is no specific statistical criteria to evaluate this hypothesis:

Treatment with pexidartinib (800 mg/day [400 mg BID]) will be well tolerated in Japanese TGCT patients.

In Part 2:

The following is the hypothesis in Part 2, but there is no specific statistical criteria to evaluate this hypothesis:

Treatment with pexidartinib (800 mg/day [400 mg BID]) will present an acceptable and manageable safety profile in Japanese TGCT patients.

There is no formal statistical hypothesis.

In June 2024, the sponsor decided not to proceed with Part 2. Therefore, the statistical hypothesis for Part 2 will not be confirmed.

9.3. Sample Size Determination

In Part 1:

Sample size was determined based on practical considerations and no formal statistical assessment has been performed. The total sample size is 3 to 6 DLT evaluated subjects.

In Part 2:

15 subjects.

The assumed ORR of the primary endpoint is 37.7% based on the ORR for pexidartinib in the ENLIVEN study. Based on the use of a one-side, exact binomial test of a proportion against the null hypothesis of 5% at the one-sided alpha = 0.05 level of significance, a sample size of 13 subjects provides more than 90% power to detect this magnitude of difference.

The sample size calculation was performed in SAS version 9.4.

9.4. Population for Analysis Sets

Analysis Sets

- The **Full Analysis Set (FAS)** will include all subjects who received at least 1 dose of pexidartinib.
- The **Safety Analysis Set** will include all subjects who received at least 1 dose of pexidartinib. The safety analysis set and FAS are identical in this study.
- The **DLT Evaluable Set** will include all subjects who received at least 1 dose of pexidartinib and experienced a DLT prior to Day 28 of Cycle 1 or completed the DLT evaluation period (Day 1 of Cycle 1 to Day 28 of Cycle 1).
- The **PK Analysis Set** will include all subjects who received at least 1 dose of pexidartinib and had measurable plasma concentrations of pexidartinib.
- The **Biomarker Analysis Set** will include all subjects who received at least 1 dose of pexidartinib and had Pdy biomarker evaluation.

The DLT evaluable set will be used for analysis in Part 1. Other analysis sets will be used both in Part 1 and Part 2.

9.5. Statistical Analysis

The SAP will be developed and finalized before database lock and will describe the subject populations to be included in the analyses, and procedures for accounting for missing, unused, and spurious data. This section is a summary of the planned statistical analyses of the primary, secondary and exploratory endpoints.

9.5.1. Efficacy Analyses

Table 3.1 lists the primary and secondary efficacy endpoints and their corresponding definitions of all endpoints. Additional details for the analysis is noted in the following sections.

In June 2024, the sponsor decided not to proceed with Part 2. Therefore, the primary efficacy analysis and the secondary efficacy analysis will be performed as the exploratory efficacy analysis using Part 1 data.

9.5.1.1. Primary Efficacy Analyses

The primary efficacy analysis will be based on the data from FAS in Part 2.

The primary efficacy endpoint is shown in Table 8.1. It will be the proportion of subjects who achieved a CR or PR (ORR) based on RECIST 1.1 by centrally reviewed MRI scan. No confirmation (ie, CR or PR at the subsequent MRI assessment) will be required for a CR or PR. The estimate of the proportion and two-sided 95% CI based on the Clopper-Pearson method will be provided.

Additional subgroup analyses to assess the homogeneity of the treatment effect based on demographic and baseline disease characteristics may be performed; details about the subgroups to be included will be provided in the study SAP.

9.5.1.2. Secondary Efficacy Analyses

The secondary efficacy endpoints will be provided in Part 2:

- Proportion of TVS responders who achieve a CR or PR at Week 25 based on TVS by centrally reviewed MRI scan
- Mean change from baseline in ROM of the affected joint, relative to a reference standard for the same joint at Week 25
- Mean change from baseline in the PROMIS Physical Function Scale at Week 25
- Proportion of BPI responders based on the BPI Worst Pain NRS item and analgesic use by BPI-30 definition (subject who (i) experienced a decrease of at least 30% in the mean BPI Worst Pain NRS item and (ii) did not experience a 30% or greater increase in narcotic analgesic use when compared to baseline)
- Best overall response (BOR) based on RECIST 1.1 by centrally reviewed MRI scan
- BOR based on TVS by centrally reviewed MRI scan
- Duration of response (DoR) based on RECIST 1.1 by centrally reviewed MRI scan

• DoR based on TVS by centrally reviewed MRI scan

A brief description of each analysis is provided below:

- An estimate of the proportion of TVS responders and BPI responders and the two-sided 95% CI based on the Clopper-Pearson method will be calculated. Subjects who do not provide data for each endpoint will be considered to be non-responders.
- Change from baseline in ROM and PROMIS will also be summarized with point estimates and 95% CIs.
- The percentage and 95% CI will be provided for the BOR
- DoR will also be analyzed as a secondary endpoint and will be summarized only for responders based on RECIST 1.1 and TVS. For subjects who do not have radiological progression, the duration of response will be censored. Subjects not known to have experienced an event at the time of data cut-off will be censored at the date of the last tumor assessment before the cut-off date. The SAP includes additional censoring rules. The Kaplan-Meier product limit method will be used to compute the estimate and 95% CI of the median and 25th and 75th percentiles.

9.5.1.3. Exploratory Analyses

The exploratory efficacy endpoints will be provided in Part 2:

- Proportion of subjects who achieve a CR or PR (ORR) at Week 25 based on RECIST 1.1 by locally reviewed MRI scan.
- Proportion of subjects who achieve a CR or PR (ORR) at Week 25 based on modified RECIST 1.1- sum of the short-axis dimension (SSD) by centrally reviewed MRI scan.
- Mean change from baseline score in the EQ-5D-5L at Week 25
- BOR based on RECIST 1.1 by locally reviewed MRI scan
- DoR based on RECIST 1.1 by locally reviewed MRI scan
- DoR based on modified RECIST 1.1-SSD by centrally reviewed MRI scan

A brief description of each analysis is provided below:

- An estimate of the proportion responders based on (i) RECIST 1.1 by local and (ii) modified RECIST 1.1-SSD by central evaluation and the two-sided 95% CI based on the Clopper-Pearson method will be calculated. Subjects who do not provide data for the endpoint will be considered to be non-responders.
- Change from baseline in EQ-5D-5L will also be summarized with point estimates and 95% CIs.
- The percentage and 95% CI will be provided for BOR in the order of CR, PR, SD, PD, and NE.
- DoR will also be analyzed as a secondary endpoint and will be summarized for responders based on (i) RECIST 1.1 by local and (ii) modified RECIST 1.1-SSD by central evaluation. For subjects who do not have radiological progression, the

duration of response will be censored. Subjects not known to have experienced an event at the time of the data cut-off will be censored at the date of the last tumor assessment before the cut-off date. The SAP includes additional censoring rules. The Kaplan-Meier product limit method will be used to compute the estimate and 95% CI of the median and the 25th and 75th percentiles.

Exploratory efficacy analyses will also be performed in Part 1.

